5.2.2.2 Blood draw fill time

It is hypothesized that:

- The blood draw duration observed for blood samples (all vacutainers, at all timepoints) collected from shorter catheters will be decreased when compared to longer catheters of the same gauge.
- The blood draw duration observed for blood samples (all vacutainers, at all timepoints) collected from smaller gauge (larger bore) catheters will be decreased when compared to larger gauge (smaller bore) catheters of the same length, over time.
- The blood draw duration observed for blood samples (all catheters, at all timepoints) collected into greater volume vacutainers will be increased when compared to smaller volume vacutainers.

A linear mixed effect model will be used with blood draw fill time as response and subject as random effect. Time, device configuration (gauge, length and their interaction), Vacutainer tube volume and baseline (at D1.2) blood draw fill time will be fixed effects. Contrast based multiple comparisons will be used to compare blood draw fill time between conditions (between gauge, between length) at each timepoint. Example tables for summary statistics (overall and per time point for each Vacutainer tube volume are given in the Appendix section by Table A.9.1 and Table A.9.2, respectively. Graphical representations of distribution of blood draw time per device is provided in Figure B.5.1 and of average blood draw time is shown in the Appendix section by Figure B.5.3. Example tables for ANOVA tables (Table A.9.3) and multiple comparisons (Table A.9.4) can be found in the Appendix A

5.2.2.3 Relationship between catheter blood draw patency indwell time and presence of intra/extravenous thrombi, thrombus length, thrombus type catheter angle/tip location *in situ*, catheter length in vessel, vein depth from skin surface, C/V ratio, and vessel anatomy

Relationship, if any, will be assessed through the computation of:

1. Summary statistics stratified by indwell time considered as a discrete variable (0, 6, 24, 30, 48, 54, 72 hours)
2. Scatter plot showing time between initial Thrombus observation to time of removal per Device Configuration
3. Bar plot showing percentage of thrombus for each time point per device configuration
4. Scatter plot showing thrombus length as a function of time grouped by device configuration
5. Relationship between flush technique and presence of Thrombus
6. Summary statistics and boxplot showing time between time of initial thrombus observation and device removal per device configuration

7. Importance of covariates will be computed with Boruta algorithm with a survival random forest model (an example output from the algorithm is provided in the Appendix by Figure B.7.1).
8. Test of predictive performance for the most important features (confirmed by the Boruta algorithm) using a leave-one-out strategy

In addition to the variables used in the primary endpoint survival model (device gauge and length), investigated baseline characteristics will be:

- Venous thrombosis
- Thrombus Length
- Thrombus Type
- Angles of insertion (Acute Inferior and Superior)
- Catheter to vein (C/V) ratio
- Catheter length in vessel
- Presence of side branches and/or intravenous valves
- Age
- Gender
- Height
- Weight
- BMI
- Dominant arm
- Medical history questionnaire responses
- Exploratory endpoints:
 - Vein collapse
 - Phlebitis
 - Dislodgement
 - Extravasation
- item Screening Blood Testing (as provided by Blood Testing CRF)
 - Coagulation Panel: PT & aPTT
 - Platelet Aggregometry: ADP, TRAP & Collagen Induced Maximal Amplitude
 - Blood Screening: Blood Glucose & Triglycerides
 - Liver Panel: ALT Average Measurement & AST Average Measurement

The Boruta algorithm does not require specific formatting and generally works well with continuous and categorical variables. In some cases, it might be interesting to move from continuous format to a categorical one (e.g. age) depending on the final analysis. Categorization rules will be detailed whenever performed.

5.2.2.4 Evaluation of changes in vessel dimensions, PIVC position (insertion angle and *in situ* tip position), and haemodynamics from baseline throughout indwell time

These will be evaluated using:

- C/V ratio
- Catheter Length in Vessel (mm)
- Catheter Insertion Angle - acute inferior border angle (deg)
- Catheter Insertion Angle - acute superior border angle (deg)
- Blood Draw Time (sec)
- Blood Flow Velocity (cm/sec)
- *In situ* tip position (Mid-Stream & Wall Contact)

For each of these characteristics, summary statistics by indwell time considered as a discrete variable (0, 6, 24, 30, 48, 54, 72 hours) and line and bar plots will be generated on average for continuous and by proportion for categorical responses, respectively.

Line plots will be similar to the example provided for cfHb in Figure B.3.2 and bar plots will be similar to the example provided for Haemolysis occurrence in Figure B.4.1, both represented in Appendix B.

Mixed effect models will be used with corresponding response and subject as random effect. Time, gauge, length, Vacutainer tube volume and baseline measurement of response will be fixed effects. Depending on the type of the response variable, the models will be:

- Linear: C/V ratio, catheter length, catheter insertion angles and blood flow velocity
- Logistic: Tip positions

Depending on model results, contrast based multiple comparisons will be used to compare means between conditions (between gauge, between length) at each timepoint. Results will be provided in Tables similar to the example given for Blood Draw Fill time in Tables A.9.3 and A.9.4, as can be found in the Appendix A.

The relationship between C/V ratio and Blood Draw Time as well as between C/V ratio and Blood Flow Velocity will be investigate using relevant graphical representation (scatter plots) and measure of association.

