2.8.2 Secondary Endpoints

- Haemolysis measured in three different ways with cfHb, AU480 and visual assessment: Quantification of cell free hemoglobin and frequency of samples exceeding a concentration of 50 mg/dL.
- Blood draw fill time. Defined as the duration from attachment of vacutainer to time when blood fills to pre-defined fill level. It is measured in seconds.
- Relationship, if any, between catheter blood draw patency indwell time and presence of intra/extravenous thrombi, catheter angle/tip location *in situ*, catheter length in vessel, vein depth from skin surface, C/V ratio, and vessel anatomy assessed via the incidence of:
 - Intravenous thrombus (mural, at tip)
 - Vein collapse
 - Presence and location of a valve relative to catheter tip
 - Side branches relative to catheter tip detected through ultrasound
- Evaluation of changes in vessel dimensions (Catheter to vein ratio), PIVC position (insertion angle and *in situ* tip position), and hemodynamics from baseline throughout indwell time evaluated using:
 - Vessel diameter or Catheter to vein ratio (C/V ratio)
 - Blood flow velocity
 - *In situ* tip position
 - Extravenous thrombus visually observed upon device removal within:
 - * Catheter hub
 - * Needleless connector
 - * Extension tubing via visual observation

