5.1.3 Blood draw fill time

The blood draw fill time (seconds) will be calculated manually using a stopwatch - from connection to blood reaching predetermined fill line.

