5.2.1 Statistical Analysis of Primary Endpoint

5.2.1.1 Indwell Time

It is hypothesized that:

- PIVC indwell time will be greater for longer catheters
- PIVC indwell time will be greater for catheters of smaller gauge (larger bore)

In order to test these hypotheses, catheter indwell time will be assessed using survival analysis, including:

- Kaplan-Meier survival curves including Log-Rank test p-value
- Cox Proportional Hazards Model with Hazard Ratios for each device vs. default device condition (BD Nexiva 20G x 1 inch) and associated 95% Confidence Intervals. Effect of the following covariates will be investigated: gender, age, BMI and dominant arm.

Main analysis will be performed stratified by device, depending on the results pooled analyses by gauge or by catheter length might be performed. An example of the Kaplan-Meier curve and associated metrics is provided in Appendix B by Figure B.1.1. An example of the Hazard Ratios extracted from the Cox Proportional Hazards models is provided in Appendix A by Table A.4.2.

For the purpose of this survival analysis, device failure (inability to flush or draw blood, see section 6.6) will be identified as follows:

- Blood Draw: Variables DEBLDCS equal to “N” and DEBLDRS equal to “N” from table INBCINBC
- Flush: Variables DEFLSSU equal to “N” and DEFLSRS equal to “N” from table INFL

Failure can occur during any of the 7 repeats of the blood draw (for either tube volumes) or flush processes, as highlighted in orange on Table 2.7.1, for right or left arm, per randomization schedule. Date-time of failure is then given by the aggregation of variables DEDTN & DEFTM, from tables INBCINBC or INFL, respectively for blood draw or flush.

Additional Indwell Time summary statistics and graphical representation will be provided as represented in Appendix A by Table A.4.1 and in Appendix B by Figure B.2.1, respectively.

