5.2.5 Approaches and Analyses for Missing Data and Other Data Issues

[figure not shown]
Missing data will not be imputed and will be considered missing for data analysis, resulting in a possible reduced sample size.

6 Summary of General Study Data

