		Mean	102.86	103.11	100.07	97.88	100.64
		95% Mean CI	99.28, 106.87	101.19, 104.96	95.85, 104.16	94.85, 101.24	98.86, 102.44
		Median	103.15	103.39	99.95	94.68	101.98
		SD	7.06	3.96	9.59	7.48	7.60
		Min, Max	92.33, 118.89	96.36, 109.89	84.03, 115.48	89.66, 116.71	84.03, 118.89
		Total Count	12	16	19	20	67
6mL	48	Blood Draw Fill Time (sec)					
		Mean	99.82	102.54	100.42	100.89	101.04
		95% Mean CI	96.37, 103.42	98.47, 106.69	96.88, 103.91	97.84, 103.92	99.21, 102.87
		Median	99.01	103.16	99.16	99.86	99.71
		SD	5.52	8.37	7.45	7.13	7.25
		Min, Max	92.46, 108.6	85.27, 118.55	87.77, 113.06	87.61, 111.31	85.27, 118.55
		Total Count	8	15	16	20	59
6mL	54	Blood Draw Fill Time (sec)					
		Mean	101.97	102.69	99.12	98.57	100.21
		95% Mean CI	96.33, 107.41	99.67, 105.60	97.09, 101.31	94.83, 102.79	98.28, 102.16
		Median	104.34	102.21	98.58	97.15	100.00
		SD	7.89	5.72	3.87	8.77	6.98
		Min, Max	92.02, 112.6	91.76, 112.19	93.56, 107.26	85.32, 119.35	85.32, 119.35
		Total Count	6	13	12	18	49

Table A.9.2: Numerical Summary of Blood Draw Fill Time in seconds for each Vacutainer tube, for each time point, per Device Configuration (Gauge and Length) and Vacutainer tube and Overall continued

Tube	Time Point (hours)	Characteristic	BD Nexiva (22G x 1 inch)	BD Nexiva (22G x 1.75 inch)	BD Nexiva (20G x 1 inch)	BD Nexiva (20G x 1.75 inch)	Overall
6mL	72	Blood Draw Fill Time (sec)					
		Mean	95.07	101.64	97.92	96.13	97.57
		95% Mean CI	92.50, 97.64	94.92, 108.95	93.41, 102.73	92.96, 99.59	95.19, 100.10
		Median	94.85	104.38	97.71	95.10	95.91
		SD	3.29	10.30	7.11	6.43	7.30
		Min, Max	91.29, 99.09	90.24, 118.23	88.42, 109.56	87.75, 109.13	87.75, 118.23
		Total Count	5	7	8	13	33

Table A.9.3: ANOVA table for Blood Draw Duration linear mixed effect model

	Chisq	Df	Pr(>Chisq)	Result
(Intercept)	1829.42	1.00	<0.001	Significant
timepoint	6.47	6.00	0.372	NS
device	2.21	3.00	0.53	NS
tube	420.57	1.00	<0.001	Significant
timepoint:device	14.15	18.00	0.719	NS
timepoint:tube	5.09	6.00	0.532	NS
device:tube	2.76	3.00	0.43	NS
timepoint:device:tube	13.80	18.00	0.742	NS

Table A.9.4: Multiple Comparisons Based on linear mixed effect model for Blood Draw Duration. Sidak's adjustment for multiple comparisons was used.

Tube	Time (hours)	Contrast	Estimate	Lwr	Upr	p-value	Result
2mL	0	BD Nexiva (22G x 1 inch) - BD Nexiva (22G x 1.75 inch)	-2.48	-7.47	2.51	0.576	NS
		BD Nexiva (22G x 1 inch) - BD Nexiva (20G x 1 inch)	-1.64	-6.64	3.36	0.834	NS

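### The fill-time model sets no residual variance by tube and has no rule for tubes that never fill; on the SAP's dummy figures, per-tube intervals are about 22% too wide (2 mL) and 14% too narrow (6 mL)

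*SAP*

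**What the plan says.** Fill time is a secondary endpoint. SAP 2.8.2 gives its meaning: "Defined as the duration from attachment of vacutainer to time when blood fills to pre-defined fill level". SAP 5.1.3 gives the measurement: "The blood draw fill time (seconds) will be calculated manually using a stopwatch - from connection to blood reaching predetermined fill line". Neither section sets a maximum waiting time, or says what is recorded for a tube that stalls, fills in part, or fills only after the rescue steps listed in Table A.7.1.

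On absent values, SAP 5.2.5 says: "Missing data will not be imputed and will be considered missing for data analysis, resulting in a possible reduced sample size". Protocol 10.4 does mention imputation, but for participants who withdraw, so it supplies no rule for an unfilled tube.

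The model is given in SAP 5.2.2.2: "A linear mixed effect model will be used with blood draw fill time as response and subject as random effect". Participant is its only random effect. Its fixed effects are time, gauge, length and their interaction, tube volume and baseline fill time. Contrasts between gauges and between lengths follow at each time point. The residual variance is not described.

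The SAP expects some draws to fail. On the primary endpoint, SAP 5.2.1.1 notes: "Failure can occur during any of the 7 repeats of the blood draw (for either tube volumes) or flush processes". SAP 5.2.1.2 deals with a 6 mL attempt made after a failed 2 mL draw.

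Two general safeguards exist. SAP 5.2.4 calls for review of residual plots and for looking into transformations if assumptions fail. Protocol 10.6 calls for a check of normality.

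**The concern.** Two separate things can go wrong.

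**Variance.** A 6 mL tube takes longer to fill than a 2 mL tube, and in the example tables its fill times also vary more. A default linear mixed model fits one residual variance to both. The standard error for every per-tube contrast is then an average of the two: too large for 2 mL and too small for 6 mL. The SAP plans to read device differences tube by tube (Table A.9.4, Figures B.5.2 and B.5.4), so this feeds straight into the reported intervals and p-values.

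**Selection.** At the failing draw, the value is absent because the fill was too slow to complete. A likelihood-based mixed model allows for loss that earlier observed values predict, but not for loss caused by the unseen value itself. With a participant effect only, it also cannot learn from the earlier fill times of that particular catheter as distinct from the other arm's. If draw failures differ between devices, the comparison of completed fills is not a fair one.

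Gauge and length effects on fill time are stated hypotheses in SAP 5.2.2.2, so both matter for how that section is read.

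**Working it through.** **Part 1: the variance**

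*The plan's own figure.* Table A.9.4, 0 h, 22G x 1 inch minus 22G x 1.75 inch, 20 draws per device:
- 2 mL: −2.48 (−7.47 to 2.51), half-width (2.51 + 7.47)/2 = 4.99 s.
- 6 mL: −0.24 (−5.23 to 4.75), half-width (4.75 + 5.23)/2 = 4.99 s.

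*Pooled SDs.* These come from the device-by-time cells of Table A.9.2, as SD = √[Σ(n−1)s² / Σ(n−1)]:
- 2 mL (449 draws): 5.024 s
- 6 mL (436 draws): 7.119 s
- both tubes together: 6.145 s

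*Reproduction.* Half-width = m × SD × √(1/n₁ + 1/n₂). With the Tukey multiplier for four devices, m = 2.574, one SD for both tubes gives 2.574 × 6.145 × √0.1 = 5.00 s, against 4.99 printed. The p-value is 0.578, against 0.576 printed. The smallest cells fit too:
- 72 h, 2 mL, n = 6 and 7: 8.80 against 8.77.
- 72 h, 6 mL, n = 5 and 7: 9.26 against 9.24.

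The table is labelled Sidak, but the six-contrast Sidak multiplier (2.637) gives 5.12 s and p = 0.742, so the printed figures are Tukey's. The formula leaves out the participant effect. That is harmless here: the between-participant contrast at 0 h (−6.64 to 3.36) has half-width 5.00 s, nearly the same as the within-participant 4.99 s.

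*With each tube's own SD*, same multiplier, n = 20 and 20:

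| | 2 mL | 6 mL |
|---|---|---|
| Half-width, pooled SD | 5.00 s | 5.00 s |
| Half-width, own SD | 4.09 s | 5.79 s |
| Pooled SD / own SD | 6.145/5.024 = 1.22 | 6.145/7.119 = 0.86 |
| Coverage of a nominal 95% interval, 2Φ(1.96 × ratio) − 1 | 98.3% | 90.9% |
| Family-wise coverage, 6 contrasts | 99.1% | 88.2% |

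*Would a log scale cure it?* From Table A.9.1 the coefficients of variation are 5.05/60.10 = 8.4% and 7.14/99.67 = 7.2%. Their root mean square is about 7.8%. A pooled log SD would make 2 mL intervals about 7% too narrow and 6 mL intervals about 9% too wide. The gap shrinks and changes sign but does not close.

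**Part 2: unfilled tubes**

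Each device has 7 × 20 = 140 possible draws per tube. Fills are from Table A.9.1 and failures from Table A.5.2. Draw failure share = failures / (fills + failures).

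| Device | 2 mL slots with no fill time | Flush failures | 2 mL draw failures | 6 mL draw failures |
|---|---|---|---|---|
| 22G x 1 | 52/140 | 16 | 2/90 = 2.2% | 2/87 = 2.3% |
| 22G x 1.75 | 31/140 | 11 | 1/110 = 0.9% | 3/109 = 2.8% |
| 20G x 1 | 23/140 | 14 | 4/121 = 3.3% | 4/118 = 3.4% |
| 20G x 1.75 | 5/140 | 5 | 5/140 = 3.6% | 0/131 = 0% |

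Most absent draws follow an earlier catheter failure, usually at a flush. True draw failures are few, and the device with most absent draws (22G x 1) is not the one with most 2 mL draw failures.

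*Possible size.* Assume that the lost draws are exactly the slowest share f. This is the worst case for a given f. The mean of the completed draws then falls by SD × φ(c)/(1−f), with c = Φ⁻¹(1−f):
- 2 mL (SD 5.05): 0.25 s at f = 2%, 0.45 s at 4%, 0.55 s at 5%.
- 6 mL (SD 7.14): 0.35 s, 0.64 s and 0.78 s.

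The bias in a device contrast is the difference between two such shifts.

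**The case against.** The strongest reply is that the tables are invented data and not the plan. SAP 5.2.2.2 does not prescribe a common variance. The example model is not quite the planned one either: Table A.9.3 has no baseline term, and it keeps non-significant terms that SAP 5.2.4 would remove. Residual plots would be reviewed. This stands to the extent that the common variance is inferred from the example output, and its effect in real data cannot be known now. It does not remove the gap, because residual review comes after the fact, no variance structure is named as the remedy, and the remedy that is named (transformation) would not equalise the tubes if taken as a log.

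A second reply is that failed draws are reported elsewhere, by device, tube and day (SAP 5.2.1.2, Tables A.5 and A.6), and that duration among samples actually obtained is a legitimate quantity. That is fair if it is labelled as such and shown next to the proportion that filled. The SAP does neither in 5.2.2.2.

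A third is that this is a secondary endpoint in a feasibility study with no acceptance criteria (SAP 2.9). That limits the weight of the point but is no reason to leave out a nearly free change.

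A reader might go further and set draws against ultrasound scans (Tables A.9.1 and A.10.1: 88 of 98 for 22G x 1, 135 of 138 for 20G x 1.75, 2 mL) and infer that the worst device loses its slowest draws. The documents do not support that. Scans come before the flush, and the flush before the draw (Protocol 7.3 and 7.4; SAP Table 2.7.1). A scanned catheter that fails its flush therefore has no draw at all. Of the 10 gaps for 22G x 1, at most 2 can be failed 2 mL draws.

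**Conclusion.** The point holds in two limited parts.

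1. **Variance.** The SAP leaves the residual variance open and its example output pools the tubes. On the dummy SDs, per-tube intervals are about 22% too wide for 2 mL and 14% too narrow for 6 mL, with coverage near 98% and 91% for a nominal 95%. This rests on the dummy SDs and on the final analysis following the example. Taking the SDs of a single cell from Table A.9.2 would suggest a larger distortion, but that mixes cell-to-cell noise with the tube effect.

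2. **Unfilled tubes.** They have no rule and are dropped, though slow by nature. At draw failure shares of 2% to 5%, a device's mean would be understated by at most 0.25 to 0.55 s (2 mL) or 0.35 to 0.78 s (6 mL), using the dummy SDs. Which device is affected, and by how much, is not shown.

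A reader might infer that the loss always shrinks gauge and length effects toward zero. It does not; the direction depends on the contrast. If 22G x 1 inch lost more slow draws it would look faster. That would favour the hypothesis that shorter catheters fill faster and work against the hypothesis that larger-bore catheters do.

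The primary endpoint and the sample size are not touched.

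**What to change.** In SAP 5.2.2.2:

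- Prespecify a separate residual variance for 2 mL and 6 mL tubes, or fit one model per tube. Do not rely on a log scale alone.
- Add a random effect for catheter within participant.
- State how unfilled, partly filled and rescued draws are recorded and analysed.
- Report the proportion of attempted draws that filled, by device and tube, beside the fill-time estimates, and label those estimates as conditional on filling.
- Add a sensitivity analysis that ranks attempted but unfilled draws as slowest, or censors them at elapsed stopwatch time where that is recorded. Leave out sessions where a failed flush meant that no draw was attempted.
- Make the adjustment named in Table A.9.4 agree with the one used.

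Censoring at the failure date-time in SAP 5.2.1.1 (DEDTN with DEFTM) should not be assumed to work. It is a clock time and not seconds since connection, and rescue steps may fall in between.

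The cost is SAP wording, a changed model call, one extra table and one sensitivity analysis. Ranking needs no new data, since draw failures are already captured for the primary endpoint; censoring needs the stopwatch time at which a draw was abandoned.

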4 STUDY DESIGN

4.1 Overall Design

This is a randomized, single-center, open-label feasibility trial to provide preliminary signals of performance to help make decisions about whether to continue with the development of product enhancements. Four variations of the BD Nexiva PIVC (20G x 1, 20G x 1.75, 22G x 1, or 22G x 1.75) will be placed in the lower cephalic vein of both arms in approximately 40 healthy volunteers; 20 participants with 20G x 1 inch and 20G x 1.75 inch catheters, and second group of 20 participants with 22G x 1 inch and 22G x 1.75 inch catheters. PIVC indwell time will be monitored (removal at 72 hrs or upon inability to flush/aspirate) with blood collected by venipuncture (Day 1 only) and via the devices using 2 and 6mL vacutainers throughout the remainder of indwell time.

After 5 participants have completed their final visit, the in-situ catheter positions will be compared to the expected tip position based on the catheter lengths (1 inch versus 1.75 inch for either gauge). Tip position of the longer catheter is expected to reside more horizontally within the vessel. In the event catheter tip position differences are not distinct between catheter device lengths study conduct may be stopped. Additionally, this analysis will be used to refine study logistics associated with device placement, securement, sonographic measurements, and blood sample acquisition/testing over the 72-hour study duration.

Each participant will complete 6 visits: a Screening Visit (V1), followed by 4 Visits (V2-V5) to be started within 30 days after screening, and a 24-96 hour follow-up post catheter removal (V6).

The duration of the study execution is expected to be 5 months.

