2.8 Endpoints

2.8.1 Primary Endpoint

The primary endpoint is the catheter indwell time, defined as the time from catheter insertion to time of catheter failure. It is measured in hours.

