subjID	gauge	bloodDisorderClotting	cancer	heartDisease	highBloodPressure	diabetesType2
S001	22G	No	No	No	No	Yes
S002	20G	No	No	No	No	No
S003	20G	No	No	No	No	No
S004	22G	No	No	No	Yes	No
S005	22G	Yes	No	No	No	Yes
S006	20G	No	No	No	Yes	No
S007	20G	No	No	No	No	No
S008	22G	Yes	No	No	No	Yes
S009	22G	No	No	No	No	Yes
S010	22G	No	No	No	No	No
S011	20G	No	No	No	No	Yes
S012	20G	No	No	No	No	No
S013	20G	No	No	No	Yes	No
S014	22G	No	No	No	No	No
S015	20G	No	No	No	Yes	No
S016	22G	No	No	No	No	No
S017	20G	No	No	No	Yes	No
S018	22G	No	No	No	No	No
S019	22G	No	No	No	No	No
S020	20G	No	No	No	Yes	No
S021	22G	No	No	No	No	No
S022	20G	No	Yes	No	Yes	No
S023	22G	No	No	No	No	No
S024	20G	No	No	No	No	No
S025	20G	No	No	No	Yes	No
S026	20G	No	No	No	No	No
S027	22G	No	No	No	No	Yes
S028	22G	No	Yes	No	No	No
S029	20G	No	No	No	No	No
S030	20G	No	No	No	No	No
S031	22G	No	No	No	No	No
S032	22G	No	No	No	No	No
S033	22G	No	No	No	No	No
S034	20G	No	No	No	No	No
S035	22G	No	No	No	No	Yes
S036	20G	No	No	No	No	No
S037	20G	No	No	No	No	No
S038	20G	No	No	No	No	No
S039	22G	No	No	No	No	No
S040	22G	No	No	No	No	No

Table C.0.4: Dummy Baseline listing (rows 1 to 40).

subjID	gauge	tipMidStream	tipWallContact	bfv	cv_ratio
S001	22G	Yes	No	162.86	35.70
S002	20G	Yes	No	169.78	33.96
S003	20G	Yes	Yes	157.73	39.69
S004	22G	Yes	Yes	151.31	42.67
S005	22G	No	No	165.24	36.42
S006	20G	No	No	164.16	44.91
S007	20G	Yes	No	168.51	35.11
S008	22G	No	No	163.64	30.23
S009	22G	Yes	No	173.14	33.27
S010	22G	Yes	No	164.40	40.57
S011	20G	Yes	No	159.85	41.06
S012	20G	No	No	173.71	37.45
S013	20G	Yes	Yes	160.25	42.14
S014	22G	Yes	No	166.91	31.00
S015	20G	Yes	No	155.56	44.65
S016	22G	Yes	No	159.83	35.38
S017	20G	Yes	No	163.14	42.58
S018	22G	Yes	No	161.69	38.99
S019	22G	No	No	159.15	34.75
S020	20G	Yes	No	151.37	43.20
S021	22G	Yes	No	163.94	34.72
S022	20G	Yes	Yes	169.70	42.95
S023	22G	No	No	164.49	40.26
S024	20G	Yes	No	161.92	32.11
S025	20G	Yes	No	173.03	42.02
S026	20G	No	No	154.34	33.76
S027	22G	Yes	Yes	155.45	41.91
S028	22G	Yes	Yes	155.20	30.45
S029	20G	Yes	No	169.53	33.37
S030	20G	Yes	No	157.41	35.70
S031	22G	Yes	No	150.97	33.86
S032	22G	Yes	No	157.20	33.50
S033	22G	Yes	No	158.89	33.09
S034	20G	Yes	Yes	161.70	38.45
S035	22G	No	No	173.17	39.35
S036	20G	Yes	No	158.18	39.31
S037	20G	No	No	150.46	33.90
S038	20G	Yes	No	158.48	37.64
S039	22G	Yes	No	173.28	40.17
S040	22G	Yes	No	156.54	32.07

Table C.0.5: Dummy Indwell Time listing (rows 1 to 40).

subjID	device	lifeTime	indwellTime_cont	status	eventType	indwellTime_disc

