S001	BD Nexiva (22G x 1 inch)	67.20	67.20	1.00	blood_draw_6mL	72.00
S001	BD Nexiva (22G x 1.75 inch)	72.53	72.00	1.00	blood_draw_6mL	72.00
S002	BD Nexiva (20G x 1 inch)	80.58	72.00	0.00		72.00
S002	BD Nexiva (20G x 1.75 inch)	68.25	68.25	1.00	flush	72.00
S003	BD Nexiva (20G x 1 inch)	57.79	57.79	1.00	blood_draw_6mL	54.00
S003	BD Nexiva (20G x 1.75 inch)	91.75	72.00	0.00		72.00
S004	BD Nexiva (22G x 1 inch)	66.26	66.26	0.00		72.00
S004	BD Nexiva (22G x 1.75 inch)	86.02	72.00	1.00	flush	72.00
S005	BD Nexiva (22G x 1 inch)	90.85	72.00	0.00		72.00
S005	BD Nexiva (22G x 1.75 inch)	66.75	66.75	1.00	flush	72.00
S006	BD Nexiva (20G x 1 inch)	64.59	64.59	0.00		72.00
S006	BD Nexiva (20G x 1.75 inch)	69.34	69.34	0.00		72.00
S007	BD Nexiva (20G x 1 inch)	61.96	61.96	1.00	flush	54.00
S007	BD Nexiva (20G x 1.75 inch)	72.67	72.00	0.00		72.00
S008	BD Nexiva (22G x 1 inch)	35.96	35.96	1.00	flush	30.00
S008	BD Nexiva (22G x 1.75 inch)	95.55	72.00	0.00		72.00
S009	BD Nexiva (22G x 1 inch)	37.24	37.24	1.00	blood_draw_2mL	30.00
S009	BD Nexiva (22G x 1.75 inch)	22.31	22.31	1.00	blood_draw_2mL	24.00
S010	BD Nexiva (22G x 1 inch)	28.76	28.76	0.00		30.00
S010	BD Nexiva (22G x 1.75 inch)	44.98	44.98	1.00	flush	48.00
S011	BD Nexiva (20G x 1 inch)	43.29	43.29	1.00	flush	48.00
S011	BD Nexiva (20G x 1.75 inch)	93.55	72.00	0.00		72.00
S012	BD Nexiva (20G x 1 inch)	37.93	37.93	0.00		30.00
S012	BD Nexiva (20G x 1.75 inch)	83.98	72.00	0.00		72.00
S013	BD Nexiva (20G x 1 inch)	74.79	72.00	1.00	flush	72.00
S013	BD Nexiva (20G x 1.75 inch)	70.04	70.04	0.00		72.00
S014	BD Nexiva (22G x 1 inch)	73.05	72.00	1.00	blood_draw_2mL	72.00
S014	BD Nexiva (22G x 1.75 inch)	70.67	70.67	0.00		72.00
S015	BD Nexiva (20G x 1 inch)	53.34	53.34	1.00	blood_draw_2mL	54.00
S015	BD Nexiva (20G x 1.75 inch)	92.07	72.00	1.00	flush	72.00
S016	BD Nexiva (22G x 1 inch)	10.73	10.73	1.00	flush	6.00
S016	BD Nexiva (22G x 1.75 inch)	61.41	61.41	0.00		54.00
S017	BD Nexiva (20G x 1 inch)	68.60	68.60	0.00		72.00
S017	BD Nexiva (20G x 1.75 inch)	58.60	58.60	1.00	flush	54.00
S018	BD Nexiva (22G x 1 inch)	43.54	43.54	1.00	blood_draw_6mL	48.00
S018	BD Nexiva (22G x 1.75 inch)	64.02	64.02	1.00	flush	72.00
S019	BD Nexiva (22G x 1 inch)	26.92	26.92	1.00	flush	24.00
S019	BD Nexiva (22G x 1.75 inch)	82.65	72.00	0.00		72.00
S020	BD Nexiva (20G x 1 inch)	73.47	72.00	1.00	blood_draw_2mL	72.00
S020	BD Nexiva (20G x 1.75 inch)	87.35	72.00	0.00		72.00

Table C.0.6: Dummy Blood Analysis listing (rows 1 to 40).

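### SAP 5.2.2.3, items 1, 2 and 6: the descriptive summaries against indwell time do not separate catheter failure from planned removal at 72 h

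*SAP*

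**What the plan says.** SAP 5.2.2.3 lists eight items that relate thrombus, catheter position, C/V ratio and anatomy to indwell time. Three matter here.

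- Item 1: "Summary statistics stratified by indwell time considered as a discrete variable (0, 6, 24, 30, 48, 54, 72 hours"). It gives no assignment rule and no split by failure status.
- Item 2: a scatter plot of the time from first thrombus observation to removal, by device configuration.
- Item 6: "Summary statistics and boxplot showing time between time of initial thrombus observation and device removal per device configuration".

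The primary endpoint is "defined as the time from catheter insertion to time of catheter failure" (SAP 2.8.1). The text does not say what value a catheter still patent at the end receives. Protocol 4.1 fixes the end: "PIVC indwell time will be monitored (removal at 72 hrs or upon inability to flush/aspirate"). SAP 5.2.1.1 says when failure is recorded: "Failure can occur during any of the 7 repeats of the blood draw (for either tube volumes) or flush processes". Table 2.7.1 puts the last of these sessions at T+72 h and the one before at T+54 h.

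Table C.0.5, "Dummy Indwell Time listing (rows 1 to 40"), carries continuous time, status and a discrete time. One failed catheter reads "72.53 72.00 1.00 blood_draw_6mL 72.00". One that did not fail reads "BD Nexiva (20G x 1 inch) 80.58 72.00 0.00", and its discrete time is also 72.

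**The concern.** A catheter found blocked at the 72 h session and a catheter taken out working at 72 h have opposite outcomes. If both fall in one class, a factor that promotes late failure is averaged with its absence among the survivors, and the contrast between the 72 h class and earlier classes is weakened. How far it is weakened depends on the share of failures in the class, which the planning assumptions make different for the two lengths.

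Items 2 and 6 have a related but separate problem. Planned removal is not an event caused by the thrombus. A thrombus first seen at 54 h yields about 18 h whether the catheter then failed at 72 h or was removed patent, so a short interval cannot be read as quick loss of the catheter.

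Two features give these displays some weight. The Boruta output in item 7 ranks predictive importance and gives neither direction nor size of an association (note to Figure B.7.1), and the Cox model in 5.2.1.1 names only gender, age, BMI and dominant arm as covariates. The direction of a link between thrombus and loss of the catheter would therefore be seen mainly in items 1, 2 and 6. Also, SAP 2.6 sends items 1 and 2 into the preliminary analysis that informs the sponsor's decisions before database lock.

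**Working it through.** **Planning figure first.** Inputs from SAP 2.4: medians 1 and 3 days, HR 0.3333, N1 = 19, N2 = 20, accrual 0, total time 3 days, two-sided alpha 0.05, stated power 0.8054.

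- Exponential failure by 3 days: 1 − 2^(−3/1) = 0.875 and 1 − 2^(−3/3) = 0.500.
- Expected events: 19 × 0.875 + 20 × 0.500 = 26.6.
- Schoenfeld: Φ(√(26.625 × 19/39 × 20/39) × ln 3 − 1.96) = Φ(0.87) = 0.809. The Lakatos method gives 0.806.

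Both agree with 0.8054, so the exponential model with these medians is a fair basis for the next steps.

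**What the coding does.** In the 40 rows of Table C.0.5, the discrete time is 72 for 25 catheters:

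| Status | Continuous time 72.00 | Continuous time below 72 | Total |
|---|---|---|---|
| 1 (failed) | 6 | 4 (64.02, 66.75, 67.20, 68.25) | 10 |
| 0 (not failed) | 9 | 6 | 15 |

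All 40 discrete values equal the nearest nominal session. That rule also moves seven failures back to a session before the failure time, for example 57.79 to 54 and 10.73 to 6. The SAP text does not state the rule.

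**Expected make-up of the 72 h class.** With S(t) = 2^(−t/median), the failed share is [S(a) − S(72)] / S(a). Here a is the earliest failure time coded as 72: a = 54 if a failure is assigned to the session that finds it, and a = 63 (midway between 54 and 72) under nearest-session rounding.

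| Median | S(54) | S(63) | S(72) | Share, a = 54 | Share, a = 63 |
|---|---|---|---|---|---|
| 24 h | 0.210 | 0.162 | 0.125 | 41% | 23% |
| 72 h | 0.595 | 0.545 | 0.500 | 16% | 8% |

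With 20 catheters at each median, a = 54 gives 1.70 + 1.89 = 3.6 failures beside 2.5 + 10.0 = 12.5 patent (22%). With a = 63 it gives 0.74 + 0.91 = 1.65 failures beside 12.5 patent (12%). The shares within each median do not depend on the number of catheters.

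**Items 2 and 6.** The longest possible interval is 72 h minus the time of first observation: about 72 h for a thrombus first seen at 0 h, 48 h at 24 h, 24 h at 48 h and 18 h at 54 h. For catheters removed as planned, the interval always equals this maximum.

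**The case against.** **Item 1 may not form outcome classes.** The same phrase appears in 5.2.2.4, 5.2.3.1 and 5.2.3.2, where it reads as visit time, and Table A.10.2 tabulates thrombus by time point (80 catheters at 0 h, 47 at 72 h). On that reading nothing is pooled in item 1. This stands as a real ambiguity. Against it, Table C.0.6 has a column `Indwell Time (cat.)`, constant within a catheter, beside a separate `timepoint` column running from 0 to 72, and item 1 is listed as a way to assess the relationship with indwell time.

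**Other analyses do use failure status.** Item 7 applies a survival random forest to thrombosis, insertion angles, C/V ratio and anatomy. Section 5.2.3.1 runs Boruta at each time point with failure so far as the response. A reader might infer that the whole comparison of these factors with indwell time mixes failures with successes. The documents do not support that: the problem is confined to three descriptive items.

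**The listing is dummy data.** A reader might take 10 of 25 (40%) as an expected rate. It is not one: the six failures at 72.00 have life times above 72 h in the same rows, and six catheters with status 0 stop before 72 h. The listing shows only that the coding permits overlap.

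**The SAP claims little for these displays.** Item 1 names no reference class, no test and no breakdown by device, so it cannot be said to use the 72 h class as a benchmark. Items 2 and 6 are labelled as time to removal, not time to failure, and end of study is tabulated among the reasons for removal in 5.2.3.1. All of this is fair. It limits the weight of the point, but leaves the displays without any handling of planned removals.

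**Conclusion.** The point holds as an inexpensive improvement to items 1, 2 and 6 of SAP 5.2.2.3. It does not show that the secondary objective is analysed wrongly.

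- For item 1 it is conditional on the final-indwell-time reading. The pooling then follows from the 72 h session and the 72 h removal falling at the same time. Its size, 23–41% failures for the 1-day median and 8–16% for the 3-day median, rests on exponential failure, the planning medians and an unstated rounding rule. Under either rule the share differs more than twofold between the two medians.
- For items 2 and 6 it does not depend on that reading. Planned removal is counted as an observed end, and the interval is cut off at 72 h.
- Item 7, the primary Kaplan-Meier and Cox analysis, the sample size and the power are unaffected.

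**What to change.** In SAP 5.2.2.3:

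1. State whether item 1 means final indwell time or visit time. If visit time, say so and refer to the layout of Table A.10.2.
2. If final indwell time, write the assignment rule: each failure goes to the session at which it was found. This rule keeps failures arising after 54 h in the 72 h class, so the split by status is what separates them. Report that class in two rows, failed and patent at planned removal, using the status variable already in Table C.0.5.
3. In items 2 and 6, treat planned removals as censored. Mark them with a separate symbol in the scatter plot, and give Kaplan-Meier time from first thrombus observation to failure by device configuration, with failure defined as in the primary analysis. The boxplot can stay beside it if planned removals are identified.

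Apply the same changes to items 1 and 2 in the preliminary analysis of SAP 2.6.

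The cost is one extra stratum and one Kaplan-Meier plot, with no new data. With about 20 catheters per configuration, only some of them with a thrombus, events per curve will be few and the curves imprecise. They should be read as description only.
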